5.11.5 Peripheral T-cell Characteristics

Ibrutinib and umbralisib have been described to have secondary targets of Itk and CK1ε, respectively [PMID.(22, 23) These molecules play a role in T-helper cell differentiation by promoting or inhibiting Th2 polarization, respectively. We will therefore monitor the change in T- cell characteristics using 10mL of peripheral blood in EDTA from pretreatment and day 8 and 1-month. This will include the interrogation of cytokines (IFN-y, TNF-α, IL-2, IL-4, IL-5, IL-6,

IL10, IL-13), phenotypic markers (CD3, CD4, CD25, CD45RO, CCR6, CCR7, CD27, CD127, CXCR3, HLA-DR, CD38) and intracellular transcription factors (FoxP3, T-bet, GATA3).

6.0 Measurement of Effect:

6.1 Response to therapy:

Response to therapy will be classified as complete response (CR), partial response (PR), stable disease (SD), progressive disease (PD), early death, or not evaluable. Response to therapy will be determined after cycle 2, 4, 6, 9, and 12 (+/- 7 days). After Month 12, efficacy assessments should occur at the investigators discretion.

Patients with a global deterioration of health status requiring permanent discontinuation of study treatment (taken off study) without objective evidence of disease progression will be counted as progressive disease unless a prior CR or PR has been previously documented. Every effort should be made to document the objective progression even after discontinuation of treatment. Deaths will be counted as treatment failure.

Patients will be analyzed with respect to overall survival (OS) and progression-free survival (PFS). Overall survival is defined as time from the first therapy administered on trial until death from any cause. For subjects who are still alive at the time of the study analysis or are lost to follow-up, survival will be censored at the last recorded date that the subject was known to be alive. Progression-free survival is defined as time from therapy until relapse, progression, or death from any cause. Response will be determined by the principal investigator or the co-principal investigators.

CR can be achieved at any response evaluation of umbralisib and ibrutinib.

Definitions for clinical response for patients with lymphoma are from the Lugano Response Criteria for Malignant Lymphoma.(24) Lymph node measurements should be taken from CT or the CT portion of the PET/CT. Measurement of lymphadenopathy will be determined by adding the sum of the products of the maximal perpendicular diameters of measured lesions (SDP). Measurable extranodal disease should be assessed in a manner similar to that for nodal disease. For these recommendations, the spleen is considered nodal disease. Disease that is only assessable, such as diffuse infiltration of an organ such as the stomach, bone marrow, peripheral blood, liver, lungs, or bowel by lymphoma without a discrete mass would constitute assessable, but not measurable, disease (eg, Lymph node or tumor mass greater than 1.5 cm in at least one dimension by physical exam, splenic enlargement, if the spleen is palpable, at least 3 cm below the left costal margin) will be recorded as present or absent only, unless, while an abnormality is still noted by imaging studies or physical examination, it is found to be histologically negative.

Response is based on PET/CT (Deauville 3 or less) or CT alone if CR is achieved by PET/CT.

Response criteria, modified from the Lugano response criteria. DLBCL is considered FDG avid.

Response Category	Definition	Nodal Masses	Spleen, liver	Bone Marrow
CR	Disappearance of all evidence of disease.	Mass of any size permitted if PET negative	Not palpable, nodules disappeared	Infiltrate cleared on repeat biopsy; if indeterminate by morphology, immunohistochemistry should be negative
PR Regression of measurable		≥50% decrease in SPD of up to 6 largest dominant	≥50% decrease in SPD of nodules (for single nodule	Irrelevant if positive prior to therapy; cell type should be specified

	disease and no new sites	masses; no increase in size of other nodes and one or more PET positive at previously involved site	in greatest transverse diameter); no increase in size of liver or spleen		
SD	Failure to attain CR/PR or PD	PET positive at prior sites of disease and no new sites on CT or PET			
Relapse/ Progressive disease	Any new lesion or increase by ≥50% of previously involved sites from nadir	Appearance of a new lesion(s) > 1.5 cm in any axis, ≥ 50% increase from nadir in SPD of more than one node, or ≥50% increase in longest diameter of a previously identified node > 1 cm in short axis. The lesions referred to above are required to be PET positive.	> 50% increase from nadir in the SPD of any previous lesions	New or involvement	recurrent

Abbreviations: CR, complete remission; FDG, [18F] fluorodeoxyglucose; PET, positron emission tomography; CT, computed tomography; PR, partial remission; SPD, sum of the product of the diameters; SD, stable disease; PD, progressive disease.

6.2 Complete Response (CR):

- 6.2.1 Complete disappearance of all detectable clinical evidence of disease and definitely disease-related symptoms if present before therapy.
- 6.2.2 DLBCL is a FDG-avid lymphoma: when the PET scan was positive before therapy, a post-treatment residual mass of any size is permitted as long as it is PET negative.
- 6.2.3 The spleen and/or liver, if considered enlarged before therapy on the basis of a physical examination or CT scan, should not be palpable on physical examination and should be considered normal size by imaging studies, and nodules related to lymphoma should disappear. However, determination of splenic involvement is not always reliable because a spleen considered normal in size may still contain lymphoma, whereas an enlarged spleen may reflect variations in anatomy, blood volume, the use of hematopoietic growth factors, or causes other than lymphoma. Similarly, other organs considered to be enlarged before therapy due to involvement by lymphoma, such as liver and kidneys, must have decreased in size.
- 6.2.4 If the bone marrow was involved by lymphoma before treatment, the infiltrate must have cleared on repeat bone marrow biopsy. The biopsy sample on which this determination is made must be UNMC IRB#345-16 Protocol Version 4.2 Dated 07Oct2019

adequate (with a goal of > 20 mm unilateral core). If the sample is indeterminate by morphology, it should be negative by immunohistochemistry. A sample that is negative by immunohistochemistry but that demonstrates a small population of clonal lymphocytes by flow cytometry will be considered a CR until data become available demonstrating a clear difference in patient outcome.

6.3 Criteria for Partial Response (PR). The designation of PR requires all of the following:

- 6.3.1 At least a 50% decrease in sum of the product of the diameters (SPD) of up to six of the largest dominant nodes or nodal masses. These nodes or masses should be selected according to all of the following:
 - they should be clearly measurable in at least 2 perpendicular dimensions
 - if possible they should be from disparate regions of the body
 - they should include mediastinal and retroperitoneal areas of disease whenever these sites are involved
- 6.3.2 No increase should be observed in the size of other nodes, liver, or spleen.
- 6.3.3 Splenic and hepatic nodules must regress by ≥50% in their SPD or, for single nodules, in the greatest transverse diameter.
- 6.3.4 With the exception of splenic and hepatic nodules, involvement of other organs is usually assessable and no measurable disease should be present.
- 6.3.5 Bone marrow assessment is irrelevant for determination of a PR if the sample was positive before treatment. However, if positive, the cell type should be specified (eg, large-cell lymphoma or small neoplastic B cells). Patients who achieve a CR by the above criteria, but who have persistent morphologic bone marrow involvement will be considered partial responders.
 - When the bone marrow was involved before therapy and a clinical CR was achieved, but with no bone marrow assessment after treatment, patients should be considered partial responders.
- 6.3.6 No new sites of disease should be observed.
- 6.3.7 For patients with PET scan was positive before therapy, the post-treatment PET should be positive in at least one previously involved site.

6.4 Criteria for Stable Disease (SD):

- 6.4.1 A patient is considered to have SD when he or she fails to attain the criteria needed for a CR or PR (see above), but does not fulfill those for progressive disease (see below).
- 6.4.2 The PET should be positive at prior sites of disease with no new areas of involvement on the post-treatment CT or PET.

6.5 Relapsed Disease (after CR)/Progressive Disease (after PR, SD):

Lymph nodes should be considered abnormal if the long axis is more than 1.5 cm regardless of the short axis. If a lymph node has a long axis of 1.1 to 1.5 cm, it should only be considered abnormal if its short axis is more than 1.0. Lymph nodes $\le 1.0 \times 1.0$

6.5.1 Appearance of any new lesion more than 1.5 cm in any axis during or after completion of therapy, even if other lesions are decreasing in size. Increased FDG uptake in a previously unaffected site

- should only be considered relapsed or progressive disease after confirmation with other modalities. In patients with no prior history of pulmonary lymphoma, new lung nodules identified by CT are mostly benign. Thus, a therapeutic decision should not be made solely on the basis of the PET without histologic confirmation.
- 6.5.2 At least a 50% increase from nadir in the SPD of any previously involved nodes, or in a single involved node, or the size of other lesions (eg, splenic or hepatic nodules). To be considered progressive disease, a lymph node with a diameter of the short axis of less than 1.0 cm must increase by ≥50% and to a size of 1.5 x 1.5 cm or more than 1.5 cm in the long axis.
- 6.5.3 At least a 50% increase in the longest diameter of any single previously identified node more than 1 cm in its short axis.
- 6.5.4 Lesions should be PET positive if observed in a typical FDG-avid lymphoma or the lesion was PET positive before therapy unless the lesion is too small to be detected with current PET systems (< 1.5 cm in its long axis by CT).

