3.1 Inclusion Criteria

- 1. Histologically confirmed Diffuse Large B-cell Lymphoma (DLBCL) or transformed DLBCL
- 2. Disease status defined as:
 - a. Patients with relapsed or refractory DLBCL that has relapsed post-transplant or that has been determined to be ineligible or unsuitable for transplant. Patients must have received at least one prior systemic therapy.
- 3. Patients must have measurable (≥ 1.5 cm) or evaluable disease. Baseline measurements and evaluations must be obtained within 21 days of registration to the study. Abnormal PET scans will not constitute evaluable disease, unless verified by CT scan or other appropriate imaging. Measurable disease must have at least one objective measurable disease parameter. A clearly defined, bi-dimensionally measurable defect or mass measuring at least 1.5 cm in diameter on a CT scan will constitute measurable disease. Proof of lymphoma in the liver is required by a confirmation biopsy. Skin lesions can be used as measurable disease provided bi-dimensional measurements are possible.
- 4. Adequate organ system function, defined as follows:
 - a. Absolute neutrophil count (ANC) $\geq 1.0 \times 10^9$ /L
 - i. By automated or manual review, whichever is greatest
 - b. Platelets $\geq 100 \times 10^9$ /L:
 - i. Unless due to bone marrow infiltration then eligible if platelets > 50 x 10⁹/L)
 - c. Total bilirubin \leq 1.5 x upper normal limit if documented hepatic involvement with lymphoma, or \leq 5 x upper normal limit if history of Gilbert's Disease.
 - d. Alanine aminotransferase (ALT) and aspartate aminotransferase (AST) ≤2.5 x ULN if no liver involvement or ≤5 x the ULN if documented liver involvement
 - e. Creatinine ≤2.0 mg/dL OR calculated creatinine clearance ≥50 mL/min (as calculated by the Cockcroft-Gault method, Appendix B)
- 5. ECOG performance status ≤2 or expected survival duration of > 2 months (Appendix C)
- 6. Patients must be ≥19 years of age (the age of consent in Nebraska)
- 7. Ability to swallow and retain oral medication
- 8. Women must not be pregnant or breast-feeding due to teratogenic effects of therapy.
 - a. All female patients of child-bearing potential must have a negative serum pregnancy test within 2 weeks prior to treatment to rule out pregnancy
 - b. Pregnancy testing is not required for post-menopausal or surgically sterilized women.

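### Sections 6.1 and 6.3 give different answers on whether shrinking but still measurable extranodal disease can be a partial response, and one such patient can flip an efficacy cut-off

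*Combined protocol and SAP*

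**What the plan says.** **Eligibility (3.1, criterion 3).** A nodal lesion is not required. Any bi-dimensionally measurable mass of at least 1.5 cm on CT counts, and an extranodal site is named: "Skin lesions can be used as measurable disease provided bi-dimensional measurements are possible".

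**General measurement rule (6.1).** "Measurable extranodal disease should be assessed in a manner similar to that for nodal disease". The spleen is counted as nodal.

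**PR definition (6.3).** The list is conjunctive: "The designation of PR requires all of the following".
- 6.3.1 asks for at least a 50% fall in the sum of the products of the diameters (SPD) of "up to six of the largest dominant nodes or nodal masses".
- 6.3.3 deals with two organs: "Splenic and hepatic nodules must regress by ≥50% in their SPD", or in greatest transverse diameter for a single nodule.
- 6.3.4 covers the remaining organs, with splenic and hepatic nodules excepted: "involvement of other organs is usually assessable and no measurable disease should be present".

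**Default (6.4.1).** A patient who meets neither CR nor PR, and not progression, has stable disease (SD).

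**Use (Section 10.0).** The overall response rate (ORR) counts patients whose best response is CR or PR. The trial stops if at most 1 of the first 12 respond, and the regimen is rejected if at most 5 of 24 respond.

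**The concern.** The protocol enrols patients with measurable extranodal lesions and says those lesions are to be assessed much like nodes. Its PR list then gives them no literal route to a PR short of the lesion ceasing to be measurable. The same scan is therefore a response or not depending on which paragraph the assessor follows.

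ORR is a secondary objective, but response is the only input to the two-stage efficacy rule. Time to response and duration of response depend on the same classification. With cut-offs of 1 of 12 and 5 of 24, a single patient can decide whether the trial stops or the regimen is rejected.

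**Working it through.** **Step 1. Apply both rules to the same patient.** These are hypothetical cases.

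*Patient 1:* one soft-tissue or skin mass, no nodal disease, 5 × 4 cm at baseline and 3 × 2 cm on treatment, still PET positive. The diameter product goes from 5 × 4 = 20 to 3 × 2 = 6, a fall of (20 − 6)/20 = 70%.

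| Text applied | Result |
|---|---|
| 6.1, lesion treated like a node | Fall exceeds 50%: PR |
| 6.3.1, literal | No node to measure: not met |
| 6.3.4, literal | Measurable disease remains: not met |
| 6.4.1, after 6.3 fails | SD, non-responder |

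*Patient 2:* a 70% nodal SPD reduction plus a lung mass that shrinks but is still measurable. Item 6.3.1 is met and 6.3.4 is not, so the literal result is again SD.

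The conflict is confined to PRs. Under 6.2.2 a residual mass that has become PET negative can still be a CR. Splenic and hepatic nodules are exempt from 6.3.4 and handled by 6.3.3, although a patient with liver nodules alone still has no node on which to satisfy 6.3.1.

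**Step 2. Look for text that settles it.** The PR row of the response table in 6.1 defines PR as regression of measurable disease and speaks of dominant masses, which favours the 6.1 reading. However, its site columns cover only nodal masses, spleen and liver, and bone marrow; none is extranodal. No sentence ranks 6.1 against 6.3.

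**Step 3. Reproduce the plan's power.** For true response rate p, the chance of passing both stages is

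P(pass) = Σ (a = 2 to 12) Bin(a; 12, p) × P(Y ≥ 6 − a), with Y ~ Bin(12, p).

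At the plan's good-regimen rate p = 0.31 this gives 0.781, about 2 points below the stated 80%. The chance of stopping at stage 1 is 0.074.

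**Step 4. Illustrate the effect of the literal reading.** Inputs:
- p = 0.31 (Section 10.0).
- PR share of responses 0.6: 3 PRs among 5 DLBCL responders in the phase I ibrutinib study described under the clinical activity of ibrutinib. Carrying this over to the combination is an assumption.
- f, the share of partial responders with residual measurable extranodal disease: assumed, since the documents give no figure.
- Every affected patient is read literally: assumed.

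Observed rate = 0.31 × (1 − 0.6f).

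| f | Observed ORR | P(pass) | P(stop at stage 1) |
|---|---|---|---|
| 0 | 0.310 | 0.78 | 0.07 |
| 10% | 0.291 | 0.72 | 0.10 |
| 20% | 0.273 | 0.65 | 0.12 |
| 30% | 0.254 | 0.57 | 0.15 |
| 40% | 0.236 | 0.49 | 0.19 |

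**Step 5. Vary the assumptions.** If only half the affected patients are read literally, f = 20% acts like f = 10% and P(pass) is 0.72 instead of 0.65. If f applies to all responders, so that the observed rate is 0.31 × (1 − f), P(pass) is 0.68, 0.55 and 0.41 at f = 10%, 20% and 30%.

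**The case against.** The best defence is that a workable reading exists. The 6.1 sentence is a general measurement rule placed ahead of the category definitions, so measurable extranodal masses could simply enter the 6.3.1 sum. Item 6.3.4 is softly worded and can be read as describing organ involvement that is assessable but not measurable, a distinction 6.1 itself draws. The table row leans the same way. Response is read by the principal or co-principal investigators at one centre, which limits differences between readers. ORR is secondary to safety.

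Much of this stands: an assessor could reasonably follow 6.1. But 6.3 still makes every item necessary, 6.3.1 still names only nodes, and nothing says the softer reading prevails. A single centre may reduce variation between readers, but it does not fix which rule they use. And although ORR is secondary, it alone drives the efficacy rule.

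A reader might go further than the documents allow in two ways:
- *That patients with evaluable disease only can never be a PR.* Item 6.3.5 makes a PR of a patient who otherwise meets CR but has persistent marrow involvement, or whose baseline marrow involvement was not re-examined. Marrow is one of the assessable, non-measurable sites listed in 6.1, so the route is open to such patients.
- *That the plan biases ORR downward by a known amount.* The downward shift arises only where the literal reading is used, and its size rests on an f that has no source in the documents.

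**Conclusion.** The contradiction holds. Criterion 3 and 6.1 treat measurable extranodal lesions as lesions whose shrinkage counts; 6.3.1 and 6.3.4, read literally, do not. It would be too strong to say that such a patient is not a responder under this protocol: the patient is SD under 6.3 and PR under 6.1, and the documents do not choose.

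The firm consequence is that one patient's classification can change the stage 1 decision (1 versus 2 of 12) or the final decision (5 versus 6 of 24). The fall in P(pass) from 0.78 to between 0.72 and 0.49 is an illustration, conditional on the 60% PR share, f between 10% and 40%, and uniform literal reading. This is a stated rule that can give the wrong result, and it should be corrected before response is used in the efficacy rule.

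**What to change.** Reconcile 6.3 with 6.1:
1. In 6.3.1, refer to measurable lesions, nodal and extranodal, in place of nodes and nodal masses.
2. In the PR row of the response table, under the nodal-masses column, state that the dominant masses counted (up to six) include measurable extranodal lesions.
3. Limit 6.3.4 to non-measurable, assessable organ involvement and delete its clause on measurable disease.
4. Leave 6.3.5 unchanged, so that the marrow-based PR survives. Do not add a rule restricting evaluable-only patients to CR, SD or PD, which would contradict it.
5. Optionally, report ORR also in patients with measurable disease at baseline.

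Apply one rule to all patients. If responses have already been read, report ORR under both readings, so that a definition settled after the event does not silently change a go/no-go result.

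The cost is small: a wording amendment and possible re-scoring of existing assessments. Lesions visible on the scheduled scans need no new imaging. Section 7.0 lists no skin-lesion measurement, so skin lesions would have to be measured and recorded at the physical examinations already scheduled; where past measurements were not recorded, re-scoring may not be possible.

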5.10 Assessments

5.10.1 Disease Assessment Schedule

A dedicated PET/CT Response assessment will be done after cycles 2, 4, 6, 9, and 12 (+/- 7 days). After Month 12, efficacy assessments should occur at the investigators discretion. If a PET/CT CR (Deauville 3 or less) is seen then a CT of chest, abdomen, and pelvis with contrast can be substituted.

A restaging bone marrow biopsy may be done if a staging bone marrow biopsy was previously positive or if symptoms suggest involvement.

Patients with stable disease after 6 cycles can continue treatment if the treating investigator feels the subject is deriving benefit. Patients with progressive disease (PD) at any time are off study and will discontinue study treatment.

Patients achieving PR/CR or stable disease that are felt by the investigator to be deriving a benefit may continue until disease progression or for a maximum of 12 cycles (52 weeks of any treatment).

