An efficacy-stopping rule is also in place for the combination. After testing the combination on 12 patients, the trial will be terminated if </= 1 patients respond. If the trial goes on to the second stage and not discontinued due to the CTE stopping rules prior to, a total of 24 patients will be studied. If the total number responding is less than or equal to five, the regimen will be rejected. This follows a Simon two-stage design for efficacy following a minimax design with the following parameters: overall response rate for a poor regimen of 0.01, overall response rate for a good regimen of 0.31, a type I error of 0.20 and power of 80%.

Efficacy measures which will be determined include ORR, TTR, DOR, and PFS. ORR is defined as the percentage of patients achieving a best response of CR/CR, PR at any disease assessment time point. TTR is defined as the time or number of cycles between study registration and documentation of first response (CR/Cru, or PR). DOR is defined as the time or number of cycles between documentation of first response and progression, change of therapy, death, or date of last contact (if still alive without progression). PFS is defined as the time between study registration and documented progression or death if no progression was observed.

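### A PET-negative patient who misses a non-marrow CR item is barred from PR and gets conflicting categories (SD, not SD, or CR), so the responder count behind the efficacy rules depends on which text is read

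*Combined protocol and SAP*

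**What the plan says.** **PR.** Section 6.3 makes PR conditional on all of its items. Item 6.3.7 reads: "For patients with PET scan was positive before therapy, the post-treatment PET should be positive in at least one previously involved site". The nodal column of the PR row in the response table repeats this. The condition covers nearly everyone, because the plan treats DLBCL as FDG avid and requires a baseline PET/CT (Section 5.1; Section 7, footnote 4).

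**CR.** A negative PET is not enough. Clinical evidence and definitely disease-related symptoms must be gone (6.2.1). A spleen or liver enlarged before therapy "should not be palpable on physical examination and should be considered normal size by imaging studies", lymphoma nodules must have disappeared, and other enlarged organs must have shrunk (6.2.3). Involved marrow must have cleared (6.2.4).

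**SD.** 6.4.1 and the table's definition column make SD the remainder: not CR, not PR, not PD. 6.4.2 and the table's nodal column add a PET condition: "The PET should be positive at prior sites of disease with no new areas of involvement".

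**Marrow.** 6.3.5 makes an otherwise complete responder with persistent marrow disease a partial responder. It does the same after a clinical CR where the marrow was involved before therapy, "but with no bone marrow assessment after treatment, patients should be considered partial responders".

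**Deauville.** Section 5.10.1 says: "If a PET/CT CR (Deauville 3 or less) is seen then a CT of chest, abdomen, and pelvis with contrast can be substituted". Section 5.1 and footnote 4 of Section 7 also label Deauville 3 as CR. The sentence just above the response table bases response on a PET/CT score of Deauville 3 or less.

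**Use of the count.** Section 10 defines ORR as best response of CR or PR at any assessment. Stage 1: "After testing the combination on 12 patients, the trial will be terminated if </= 1 patients respond". Final: "If the total number responding is less than or equal to five, the regimen will be rejected". If the trial continues, "a total of 24 patients will be studied".

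**The concern.** A patient whose PET has turned negative has had a deep metabolic response. If the spleen is still enlarged, 6.2.3 withholds CR and 6.3.7 withholds PR. The protocol foresees this patient: 6.2.3 itself notes that an enlarged spleen can have causes other than lymphoma. Under 6.4.1 the patient falls to SD, which is not a response. Under the Deauville wording the same patient is a complete responder.

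Section 6.1 leaves the call to the principal or co-principal investigators, with no rule for choosing between the texts. With cut-offs of 1 in 12 and 5 in 24, one patient can move an efficacy decision, and shifts ORR by 1/24 = 4.2 percentage points. The same choice fixes the date of first response, which ends TTR and starts DOR. If the reading is chosen after responses are seen, the choice is data-driven.

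**Working it through.** **Step 1: the texts side by side.** Take a patient with a positive baseline PET, a negative PET now (taken here as Deauville 3 or less), no new sites, and an enlarged spleen as the only CR item missed.

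| Text | Result | Counted in ORR? |
|---|---|---|
| 6.2.3 | not CR | – |
| 6.3 with 6.3.7; PR table row | not PR | – |
| 6.4.1; SD definition in table | SD | no |
| 6.4.2; SD nodal column in table | not SD | – |
| 5.1, 5.10.1, sentence above the table, Section 7 footnote 4 | CR | yes |

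The same holds for residual nodules or other enlarged organs (6.2.3) and for residual clinical evidence or symptoms (6.2.1). If marrow is the only item missed, 6.3.5 gives PR, which is counted. Read literally, even that clashes with the requirement to meet all PR items, since 6.3.7 fails.

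**Step 2: the plan's own figure.** Inputs from Section 10: stop if 1 or fewer of 12 respond; reject if 5 or fewer of 24; good-regimen rate 0.31; power 80%. With b(x; n, p) the binomial probability and Y ~ Bin(12, p),

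P(pass) = Σ (x = 2 to 12) b(x; 12, p) · P(Y ≥ 6 − x).

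At p = 0.31 this is 0.781, close to the stated 80%. The early-stop probability, P(X ≤ 1 of 12), is 0.074. The stated type I error of 0.20 at a poor-regimen rate of 0.01 does not reproduce (the result is about 0). That is a separate matter and is not used here.

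**Step 3: a share of responders uncounted.** Let m be the share of true responders who are PET negative, miss a non-marrow CR item, are called SD and never qualify at another scan. The documents give no value, so m is an assumption. The counted rate is 0.31 × (1 − m).

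| m | Counted rate | P(pass) | P(early stop) |
|---|---|---|---|
| 0 | 0.3100 | 0.781 | 0.074 |
| 5% | 0.2945 | 0.732 | 0.091 |
| 10% | 0.2790 | 0.676 | 0.111 |
| 20% | 0.2480 | 0.547 | 0.162 |
| 30% | 0.2170 | 0.406 | 0.230 |

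**Step 4: exactly one responder uncounted at the final look.** Seven true responders are then needed instead of six. At 0.31, P(pass) falls from 0.781 to 0.643. The difference, 0.139 before rounding of the two terms, is the chance of exactly 6 of 24 with stage 1 passed.

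**The case against.** The strongest reply is that the plan does classify this patient. 6.4.1 and the table define SD as the remainder, so a reader who infers that such a patient fits no response category goes too far. That stands: the defect is a conflict between 6.4.1, 6.4.2 and the Deauville wording, not an empty cell.

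A reader might also infer that missing any CR item causes the loss. The documents do not support that. 6.3.5 expressly sends persistent or unassessed marrow to PR, and a specific rule is naturally read as an exception to 6.3.7.

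The loss is not certain either. The Deauville sentence above the response table sits inside Section 6 and points to CR, so the patient may well be counted. The caution in 6.2.3 about enlarged spleens gives an assessor some ground for not denying CR on size alone. Disease-related symptoms with a negative PET would be unusual. ORR takes the best response over assessments after cycles 2, 4, 6, 9 and 12, so a patient who was a PET-positive PR earlier, or a full CR later, is counted anyway.

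Finally, the chance that the count sits exactly on a cut-off is not the size of this defect. P(6 of 24) is 0.155, 0.185 and 0.150 at ORR 0.20, 0.25 and 0.31 (0.143, 0.171 and 0.139 with stage 1 passed). It would be the same for any one-patient error.

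All of this limits frequency and direction. None of it says which text governs.

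**Conclusion.** The criteria are wrong as written for one group: patients with a positive baseline PET who become PET negative and miss a non-marrow CR item. They cannot be PR, and the plan calls them SD, not SD, or CR depending on the section. Under the SD reading, those who never qualify at another assessment drop out of ORR.

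The size rests on an assumed frequency. At a true ORR of 0.31, losing 5 to 10% of true responders lowers the chance of passing from 0.78 to between 0.73 and 0.68. Losing one at the final look lowers it to 0.64. Under the Deauville reading nothing is lost, but the extra CR items in 6.2 are then bypassed.

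A reader might infer that this decides the trial. It does not: the primary objective is safety, with its own stopping rule based on cumulative toxicity events. What is affected is the efficacy stop, the regimen rejection, ORR, TTR and DOR.

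**What to change.** Before responses are counted, reconcile 6.2, 6.3.7, 6.4.1, 6.4.2, the response table and the Deauville statements (Section 5.1, Section 5.10.1, the sentence above the response table, Section 7 footnote 4) so that each PET-negative patient has one category.

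One workable form:
- Add to 6.3 that a patient with no new sites who is PET negative at all prior sites but misses another CR item counts as a responder, at least PR, notwithstanding 6.3.1 and 6.3.7. This extends what 6.3.5 already does for marrow. It should cover every non-marrow CR item: spleen and liver size, residual nodules, other enlarged organs, clinical evidence and symptoms. 6.3.1 has to be named because 6.2.2 allows a PET-negative mass of any size, while 6.3.1 demands a 50% reduction. Say also whether the nodule item, 6.3.3, still applies.
- State that 6.4.2 and the SD nodal cell do not override the residual definition in 6.4.1, or the reverse.
- Make the Deauville statements refer to CR as defined in 6.2.

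Assigning CR instead would also resolve the conflict, provided 6.2 is changed to match. The cost is a few sentences and cross-references, with no extra scans or patients.
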